4.4. Pharmacokinetic Evaluations

All tabulations of PK data will be presented in a separate report appended to the CSR.

4.5. Safety Analyses

Safety analyses will be conducted using the ITT analysis set.

4.5.1. Study Drug Exposure

Duration of infusion will be summarized using descriptive statistics. A summary of the numbers and percentages of subjects with a dose interruption will be provided. Duration of interruption will be summarized using descriptive statistics. Summary statistics will be provided for the total drug amount received by the subject and the total volume infused.

All data related to study medication administration, including details on inpatient hospitalization for dosing, will be presented in a data listing.

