#### **5.8** Measurement of Patient Compliance

Patient compliance with study drug administration is dependent on the proper preparation and administration of IV infusions by study center personnel. Because the study drug will be administered by study staff as an IV infusion, treatment compliance will be verified by observation in the clinic by study staff. Treatment will be considered completed if 80% or more of each of the doses (based on total volume of the IV solution) has been administered to the patient.

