### **8.8** Action Taken for Adverse Event

Action taken in regards to study medication will be defined as:

- None;
- Infusion interrupted and restarted at a later time;
- Infusion stopped and was not restarted at a later time.

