### 9.2.3 Safety Analyses

A summary of study drug exposure, including the duration of the infusion and dose, and the proportion of patients with modifications in the duration of infusion will be produced.

Adverse events will be summarized by MedDRA system organ class and preferred term. Separate tabulations will be produced for all treatment emergent AEs, treatment-related AEs (those considered by the Investigator as at least possibly drug related), SAEs, and discontinuations due to AEs. By-patient listings will be provided for deaths, SAEs, DLTs, and events leading to discontinuation of treatment.

Descriptive statistics will be provided for clinical laboratory data, including cytokines, as well as vital signs data, presented as both actual values and changes from baseline relative to each on-study evaluation and to the last evaluation on study.

Descriptive statistics will be provided for ECG interval data and presented as both actual values and changes from baseline relative to each on-study evaluation and to last evaluation on study.

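### SAP 4.5.1 replaces the protocol's proportion of patients with modified infusion duration by a narrower, undefined count of dose interruptions without declaring the change, and tabulates no delivery of each assigned dose

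*SAP*

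**What the plan says.** On exposure, protocol 9.2.3 asks for infusion duration and dose, and says that "the proportion of patients with modifications in the duration of infusion will be produced".

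SAP 4.5.1 keeps the duration ("Duration of infusion will be summarized using descriptive statistics") but the count becomes "A summary of the numbers and percentages of subjects with a dose interruption will be provided", with a summary of how long interruptions lasted. For amounts it says: "Summary statistics will be provided for the total drug amount received by the subject and the total volume infused". It ends with a listing: "All data related to study medication administration, including details on inpatient hospitalization for dosing, will be presented in a data listing".

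Three other places bear on this:

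- Protocol 8.8 sets the action codes for adverse events. Besides no action, it separates an infusion interrupted and later restarted from "Infusion stopped and was not restarted at a later time".
- Protocol 5.8 defines completion dose by dose and by volume: "Treatment will be considered completed if 80% or more of each of the doses" has been given.
- SAP 1.1.2 undertakes to set out differences from the protocol. SAP section 5 reports none.

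**The concern.** The SAP has swapped one summary for a narrower one without saying so. The primary objective is the safety and tolerability of multiple doses, and whether infusions ran as planned is a direct measure of tolerability. If interruption means what protocol 8.8 suggests, the exposure table counts pauses but not infusions abandoned or run longer without a pause. In cohorts of three, one patient is 33%, so the choice of definition can change the reported figure.

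The amount measures raise a second question. Cohorts are defined in µg/kg and completion is defined per dose, but the planned summaries are totals, apparently per subject over both doses. A total does not show whether each assigned dose was delivered.

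**Working it through.** There is no sample size or power figure to reproduce. SAP 3.1 says that the sample size was not based on power calculations. The check is a comparison of text with some simple arithmetic.

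**1. Planned duration.** Protocol 5.6 gives 60 minutes at about 3.3 mL/min: 60 × 3.3 = 198 mL. The alternative rate gives 15 × 1.1 + 55 × 3.3 = 16.5 + 181.5 = 198 mL in 70 minutes. Both agree with the roughly 200 mL bag in protocol 5.2. A modification can therefore be judged against 60 or 70 minutes, depending on the regimen.

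**2. What each count captures.** The middle columns read the protocol 9.2.3 measure as any departure from planned duration, and interruption as in protocol 8.8.

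| Event | Protocol 9.2.3 | SAP 4.5.1 interruption | Other SAP output |
|---|---|---|---|
| Paused, then restarted (including at a slower rate) | counted | counted | duration statistics |
| Lengthened without a pause | counted | not counted | duration statistics only |
| Stopped for good because of a TEAE | counted | not counted | TEAE discontinuation count (SAP 4.5.2); Table 14.3.2.3 |
| Stopped for good for another reason | counted | not counted | listing only, plus a short duration |

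The first row includes slowing after an acute reaction, because protocol 5.11 and Appendix 1 stop the infusion before resuming it more slowly. The second row exists because protocol 5.6 allows extension up to 3 hours without mentioning a stop.

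**3. Effect on a cohort (illustrative durations).** Take three infusions of 60, 60 and 10 minutes, the last abandoned.

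- Mean = (60 + 60 + 10)/3 = 43.3 minutes; minimum 10, median 60, maximum 60.
- Interruptions: 0/3. Modified duration: 1/3 = 33%.

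**4. Total amount.** At 300 µg/kg (0.3 mg/kg), with an assumed 50 kg patient and the documents' 104 kg dosing cap:

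- 50 kg, two full doses: 50 × 0.3 × 2 = 30.0 mg.
- 104 kg, half of each dose: 104 × 0.3 × 2 × 0.5 = 31.2 mg.

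The half-dosed patient shows the larger total.

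**5. Total volume.** Two full infusions are about 2 × 200 = 400 mL.

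| Dose 1 + Dose 2 | Total volume | Share of 400 mL | At least 80% of each |
|---|---|---|---|
| 100% + 60% | 200 + 120 = 320 mL | 80% | no |
| 80% + 80% | 160 + 160 = 320 mL | 80% | yes |
| 70% + 90% | 140 + 180 = 320 mL | 80% | no |

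Total volume shows an overall shortfall but not which dose fell short, nor whether the criterion was met.

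**6. Scale.** The maximum is 4 × 3 + 5 × 3 = 27 patients, or 54 infusions at two each.

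**The case against.** The strongest reply is that little safety information is lost, and most of it stands.

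- A reader might infer that permanently stopped infusions go uncounted altogether. They do not. SAP 4.5.2 counts subjects with a TEAE leading to discontinuation of study medication, with a severe TEAE, or with a dose-limiting toxicity, and by-subject listings follow. Appendix 1 makes a severe acute reaction a dose-limiting toxicity. Only stops for other reasons lack a count.
- A reader might infer that slowed infusions are missed. Slowing after an acute reaction follows a stop and so falls under interruption. Only lengthening without a pause is left out, and it still enters the duration statistics.
- A reader might infer that the table hides an abandoned infusion behind a low mean. SAP 3.2 requires the median, minimum and maximum too, and a minimum of 10 minutes would be visible. This shows that something happened, but not how many infusions were affected once there are two per patient or cohorts are pooled under SAP 3.5.
- A reader might infer that per-dose delivery cannot be recovered. Listing 16.2.5.1 covers all administration data, and 54 infusions can be read by hand. Total volume, the basis of the 80% rule, is also summarised.

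It is also fair to say that protocol 8.8 sets adverse event codes and does not define the exposure table's term, that the protocol does not define a modification, and that it promises no table split by dose and no 80% count. That makes the per-dose table a recommendation and not a broken commitment. It does not excuse dropping the one proportion that the protocol does promise, or the statement that nothing changed.

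**Conclusion.** The point holds in limited form and is minor. SAP 4.5.1 omits a summary that protocol 9.2.3 specifies, puts an undefined and apparently narrower count in its place, and SAP section 5 does not declare it. What is actually lost is confined to the exposure table, to permanent stops not caused by a TEAE, and to extensions without a pause. The documents do not support saying that stopped or slowed infusions go unreported across the analysis, or that delivery of each dose cannot be established.

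The effect on a reported figure can still be visible: 0/3 against 1/3 in the example. Whether each dose reached 80% would have to be worked out by hand from the listing.

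This rests on four assumptions: that interruption carries the sense of protocol 8.8; that modified duration includes infusions ended early; that the SAP's totals are per subject over both doses, which is the likely reading but is not stated; and that an infusion stopped for good because of a TEAE is recorded as a discontinuation of study medication.

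**What to change.** In SAP 4.5.1 and Table 14.4.1:

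1. Restore the number and percentage of patients with any modification of infusion duration relative to the planned 60 or 70 minutes, by type: interrupted and restarted; slowed or extended; stopped and not restarted. Define each type.
2. For Dose 1 and Dose 2 separately, give the number dosed, the µg/kg received, the percentage of planned volume, and the number receiving at least 80%. State that µg/kg uses the dosing weight, so that patients at the 104 kg cap are not read as under-dosed. SAP 4.5.3 already separates the two doses for cytokines, CRP and complement Bb.
3. Keep total amount and total volume as secondary lines, with units and the doses they cover.
4. If the protocol's proportion is not restored, declare and explain the change in SAP section 5.

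The cost is some SAP wording and a slightly longer exposure table. No protocol amendment is needed. The SAP already lists all administration data; the case report form is not among the documents, so confirm that it records start, stop and restart times and volume for each infusion.

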4.5.2. Adverse Events

Adverse events will be displayed in tables and data listings using MedDRA system organ class (SOC) and preferred term.

Analyses of AEs will be performed for those events that are considered treatment-emergent, where treatment-emergent is defined per protocol as any AE with onset during or after the administration of study medication through 28 days after dosing, or any event that was present pre-infusion but worsened in intensity or was subsequently considered drug-related by the Investigator.

When determining whether an AE is treatment-emergent, partial dates will be handled as follows. If the day of the month is missing, the onset day will be set to the first day of the month unless it is the same month and year as study treatment. In this case, in order to conservatively report the event as treatment-emergent, the onset date will be assumed to be the date of treatment. If the onset day and month are both missing, the day and month will be assumed to be January 1, unless the event occurred in the same year as the study treatment. In this case, the event onset will be imputed as the day of treatment, in order to report the event conservatively as treatment-emergent. A missing onset date will be imputed as the day of treatment. If the resulting imputed onset date is later than a non-missing date of resolution, then the imputed onset date will be set to the resolution date. The imputed data is used solely for the purpose of determining whether an AE is treatment-emergent; actual dates as recorded on the eCRF will be presented in subject listings.

Adverse events are summarized by subject incidence rates; therefore, in any tabulation, a subject contributes only once to the count for a given SOC or preferred term.

The numbers and percentages of subjects with any treatment-emergent adverse event (TEAE), with any TEAE assessed by the Investigator as related to treatment (definitely or possibly related), with any TEAE that is severe in intensity, with any serious TEAE, with any TEAE leading to discontinuation of study medication, or with any TEAE considered a DLT will be summarized by dose group and overall.

Tabulations by SOC and preferred term will be produced for all TEAEs, for all related TEAEs, all TEAEs of severe intensity, all treatment-emergent IRRs, and for all serious TEAEs. In these tabulations, each subject will contribute only once (i.e., the most related occurrence or the most intense occurrence) to each of the incidence rates in the descriptive analysis, regardless of the number of episodes of a given event (preferred term). The most commonly occurring TEAEs, defined as those events experienced by at least 10% of all subjects, will be tabulated by preferred term in decreasing order in frequency.

Separate tables will present AE incidence rates by maximum relationship to study drug and by maximum severity. Subjects who report multiple occurrences of the same AE (preferred term) will be classified according to the most related or most severe occurrence, respectively.

No formal hypothesis-testing of AE incidence rates will be performed.

All reported AEs will be provided in data listings, including AEs that are not treatment-emergent.

By-subject listings also will be provided for the following: subject deaths, SAEs, AEs leading to drug discontinuation, and DLTs.

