# 2 STUDY OBJECTIVES

# 2.1 Primary Objective

• To evaluate the safety and tolerability of multiple doses of ALN-TTR02.

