1.1.2. Study Objectives

The primary objective of this study is to evaluate the safety and tolerability of multiple doses of ALN-TTR02.

The secondary objectives of this study are:

- To characterize the plasma and urine pharmacokinetics (PK) of ALN-TTR02.
- To assess preliminary evidence of the pharmacodynamic (PD) effect of ALN-TTR02 on serum total TTR levels.

This statistical analysis plan (SAP) is designed to outline the methods to be used in the analysis of study data in order to answer the study objective(s). Populations for analysis, data handling rules, statistical methods, and formats for data presentation are provided. The statistical

analyses and summary tabulations described in this SAP will provide the basis for the results sections of the clinical study report (CSR) for this trial. Pharmacokinetic (PK) and pharmacokinetic/pharmacodynamics (PK/PD) analyses will be described in a separate analytical plan, will be performed by Alnylam Pharmaceuticals or its designated Contract Research Organization (CRO), and presented in a separate report (to be included in the CSR).

This SAP will also outline any differences in the currently planned analytical objectives relative to those planned in the study protocol.

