1.2. Study Design

1.2.1. Synopsis of Study Design

Protocol ALN-TTR02-002 is a multi-national, multi-center, Phase 2, open-label, multi-dose, dose escalation study designed to determine the safety, tolerability, PK, and PD of 2 consecutive doses (separated by approximately 4 weeks) of ALN-TTR02 in patients with ATTR.

Patients of any mutant TTR genotype with a biopsy-proven diagnosis of ATTR who exhibit documented signs/symptoms of the disease (e.g., sensory, motor, or autonomic neuropathy) that are at least mild to moderate in severity will be eligible for the study, provided they have a body mass index (BMI) of 17-33 kg/m², an adequate performance status (Karnofsky performance status of 60% or greater), adequate hepatic and renal function, no active infection or inflammatory disorder, stable cardiac status, and have not had a liver transplant.

Two doses of ALN-TTR02 will be given 4 weeks apart to 4 sequential cohorts comprised of 3 patients each. The 4 cohorts will receive ascending doses of 10, 50, 150, and 300 µg/kg. No patient will be a member of more than 1 treatment group. An alternative dosing regimen of 2 doses of ALN-TTR02 (at a dose previously determined by the Safety Review Committee [SRC] to be safe and tolerable) separated by 3 weeks may be evaluated in the optional cohort(s).

Within each of the cohorts, the first patient will receive their first dose and if the dose is well-tolerated (per protocol Section 5.7.3, Dose-limiting Toxicity), Patients 2 and 3 will receive their first dose at that same dose level no sooner than 48 hours apart, with Patient 2 receiving a dose of study drug no sooner than 48 hours after the dosing of Patient 1. Similar to the first dose, the second dose will be administered to patients 4 weeks after the first dose in a sequential manner with at least 48 hours separating dosing of each patient. If after the first dose, ALT and AST are >2.5 ×ULN, that patient would not receive their second dose.

Dose escalation to the next cohort will proceed after the collective safety and tolerability data through at least 96 hours post-first dose from the 3 patients in the previous cohort has been

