4.5.3. Laboratory Data

Clinical laboratory values will be expressed in SI units.

Descriptive statistics will be provided for the actual values and changes from baseline to each on-study evaluation for each clinical laboratory parameter, including hematology, clinical chemistry, LFTs, thyroid function tests, and coagulation studies. Percent change from baseline will also be summarized.

Descriptive statistics will be provided for CRP and cytokines at pre-dose and 2, 6, and 24 hours post-dose. Change from pre-dose will also be summarized. Fold change, as defined below, will be summarized for CRP. Complement factor (Bb) will be summarized at pre-dose, and 30 minutes, 2 hours and 24 hours post-dose. Change and fold change from pre-dose will also be summarized. Separate summaries will be presented for Dose 1 and Dose 2.

Fold change from pre-dose is defined as the ratio of the post-dose value to the pre-dose value. Maximum fold change is defined as the ratio of the maximum post-dose value to the pre-dose value. Maximum fold change from pre-dose for cytokines, complement factor (Bb), and CRP will be represented graphically in the form of a semi- \log_{10} plot. Maximum fold change will be plotted for each subject, grouped by dose level. Data recorded as below the limit of detection will be set equal the lower limit of detection for the calculation of fold change. Separate plots will be presented for Dose 1 and Dose 2.

For each continuous laboratory parameter, results will be categorized as low, normal, or high based on the laboratory normal ranges. Shift tables will be employed to summarize the pre-dose category versus the post-dose category, where the post-dose category will be based on the maximum observed value (in absolute value) subsequent to each dose. For dose 1, the maximum value shall be selected from assessments performed through the Day 28 pre-dose

value (Day 21 for the 3-week regimen). All out-of-range and clinically significant laboratory results will be identified in subject data listings.

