Table 14.2.3.3A	Summary of Percent Reduction in Serum Mutant TTR (LCMS/MS) by Dose Group – Q4W Cohorts (Intent-to-Treat Analysis Set – V30M Subjects)
Table 14.2.3.3B	Summary of Percent Reduction in Serum Mutant TTR (LCMS/MS) by Dose Group – Q3W Cohorts (Intent-to-Treat Analysis Set – V30M Subjects)
Table 14.2.4.1A	Summary of Area under the TTR (ELISA) Concentration Time Curve – Q4W Cohorts (Intent-to-Treat Analysis Set)
Table 14.2.4.1B	Summary of Area under the TTR (ELISA) Concentration Time Curve – Q3W Cohorts (Intent-to-Treat Analysis Set)
Table 14.2.4.2A	Summary of Area under the Wild Type TTR (LCMS/MS) Concentration Time Curve – Q4W Cohorts (Intent-to-Treat Analysis Set – V30M Subjects)
Table 14.2.4.2B	Summary of Area under the Wild Type TTR (LCMS/MS) Concentration Time Curve – Q3W Cohorts (Intent-to-Treat Analysis Set – V30M Subjects)
Table 14.2.4.3A	Summary of Area under the Mutant TTR (LCMS/MS) Concentration Time Curve – Q4W Cohorts (Intent-to-Treat Analysis Set – V30M Subjects)
Table 14.2.4.3B	Summary of Area under the Mutant TTR (LCMS/MS) Concentration Time Curve – Q3W Cohorts (Intent-to-Treat Analysis Set – V30M Subjects)
Table 14.3.1.1	Summary of Treatment-Emergent Adverse Events, Overall and by Dose Group (Intent-to-Treat Analysis Set)
Table 14.3.1.2	Treatment-Emergent Adverse Events, Overall and by Dose Group (Intent-to-Treat Analysis Set)
Table 14.3.1.3	Treatment-Emergent Adverse Events Related to Study Drug, Overall and by Dose Group (Intent-to-Treat Analysis Set)
Table 14.3.1.4	Severe Treatment-Emergent Adverse Events, Overall and by Dose Group (Intent-to-Treat Analysis Set)
Table 14.3.1.5	Severe Treatment-Emergent Adverse Events Related to Study Drug, Overall and by Dose Group (Intent-to-Treat Analysis Set)
Table 14.3.1.6	Serious Treatment-Emergent Adverse Events, Overall and by Dose Group (Intent-to-Treat Analysis Set)
Table 14.3.1.7	Treatment-Emergent Infusion Related Reaction Signs and Symptoms, Overall and by Dose Group (Intent-to-Treat Analysis Set)
Table 14.3.1.8	Most Common ($\geq 10\%$ of All Subjects) Treatment-Emergent Adverse Events, Overall and by Dose Group (Intent-to-Treat Analysis Set)
Table 14.3.1.9	Treatment-Emergent Adverse Events by Maximum Relationship to Study Drug, Overall and by Dose Group (Intent-to-Treat Analysis Set)
Table 14.3.1.10	Treatment-Emergent Adverse Events by Maximum Severity, Overall and by Dose Group (Intent-to-Treat Analysis Set)
Table 14.3.2.1	Subject Listing of Deaths

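### The adverse-event and infusion-reaction tables do not separate Dose 1 from Dose 2, so change on re-exposure can be read only by hand from the listings

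*SAP*

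**What the plan says.** Protocol 2.1 gives the primary objective as "To evaluate the safety and tolerability of multiple doses of ALN-TTR02", and SAP 1.1.2 repeats it. Each patient is scheduled for two infusions. SAP 1.2.1 says "Two doses of ALN-TTR02 will be given 4 weeks apart to 4 sequential cohorts comprised of 3 patients each", and optional cohorts may use a 3-week interval.

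**Counting rule.** SAP 4.5.2 says that "in any tabulation, a subject contributes only once to the count for a given SOC or preferred term". Repeat episodes of a term collapse to the most related or most intense one. The sentence that sets up the overview of treatment-emergent events ends "with any TEAE considered a DLT will be summarized by dose group and overall", with no split by infusion.

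**Table list.** SAP 7.1 plans Tables 14.3.1.1 to 14.3.1.10, all overall and by dose group. The infusion-reaction table, 14.3.1.7, is titled "Treatment-Emergent Infusion Related Reaction Signs and Symptoms, Overall and by Dose Group". SAP 3.2 defines dose group by dose level, regimen and premedication; SAP 3.5 defines it by dose level and regimen. Neither definition refers to the first or second infusion.

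**Other safety data.** For CRP, cytokines and complement, SAP 4.5.3 adds: "Separate summaries will be presented for Dose 1 and Dose 2". Laboratory shifts in the same section use the post-dose value after each dose. Serial vital signs (SAP 4.5.4) and serial ECGs (SAP 4.5.5) are summarised for each dosing day.

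**Denominator.** Safety uses the ITT set (SAP 4.5), which requires study treatment but not a second dose (SAP 2.1). SAP 1.2.1 contains a liver-enzyme rule under which the second dose is not given, and Protocol 5.6 requires eligibility to be rechecked before it. The disposition summary (SAP 4.1) counts patients dosed, not patients given Dose 2.

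**The concern.** The second infusion is what makes this a multiple-dose trial. A reader of the safety section will want to know whether reactions fade, recur or worsen on re-exposure. The SAP provides that view for cytokines, complement and vital signs, but not for adverse events or infusion reactions, which bear most directly on tolerability.

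Two things are at stake. First, a reaction confined to the first infusion and one that recurs at both produce the same table entry. Second, patients who never received Dose 2 stay in the denominator for events that can only follow Dose 2. Because dosing may stop on account of how Dose 1 was tolerated, those patients are not a random subset.

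**Working it through.** **Plan's own figure.** SAP 3.1 gives 4 planned dose levels × 3 patients + 5 optional cohorts × 3 patients = 12 + 15 = 27, as stated. At two infusions each, that is at most 27 × 2 = 54 planned infusions. The study is descriptive, so no power calculation applies.

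**What one table cell can hide.** Suppose k patients are counted for a term and all received both doses. Each had the event after Dose 1 only (a patients), after Dose 2 only (b) or after both (c), with a + b + c = k. The patients affected are then a + c after Dose 1 and b + c after Dose 2. Each choice of a, b and c gives a different pair, so the number of pairs that fit the cell is (k + 1)(k + 2)/2. Patient-dose occurrences total k + c, which lies between k and 2k.

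| Patients counted (k) | Dose 1/Dose 2 pairs that fit | Patient-dose occurrences |
|---|---|---|
| 1 | 2 × 3 / 2 = 3 | 1 to 2 |
| 2 | 3 × 4 / 2 = 6 | 2 to 4 |
| 3 | 4 × 5 / 2 = 10 | 3 to 6 |
| 6 | 7 × 8 / 2 = 28 | 6 to 12 |

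In a three-patient cohort, reactions in all three at Dose 1 only (3 of 6 infusions) and in all three at both doses (6 of 6) both print as 3/3 (100%).

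**The same point with assumed rates.** The documents give no per-dose event rates, so these are assumptions, with the two doses taken as independent. The expected table entry is 1 − (1 − p1)(1 − p2), where p1 and p2 are the event probabilities after Dose 1 and Dose 2:

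- p1 = 0.20, p2 = 0.20: 1 − 0.80 × 0.80 = 0.36
- p1 = 0.36, p2 = 0: 1 − 0.64 × 1 = 0.36
- p1 = 0, p2 = 0.36: 1 − 1 × 0.64 = 0.36
- p1 = 0.30, p2 = 0.0857: 1 − 0.70 × 0.9143 = 0.36

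Equal risk, risk at one infusion only and falling risk all give 36%. That 36% is nevertheless a correct statement of the proportion affected over the course.

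**Denominator.** Take three patients, one not re-dosed, and let both re-dosed patients react only at Dose 2. The planned table prints 2/3 (67%), while incidence after Dose 2 among those who received it is 2/2 (100%).

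**Selection in the other direction.** Take three patients, one of whom reacts at Dose 1 and is not re-dosed, while the other two never react. Columns by infusion would print 1/3 (33%) and then 0/2 (0%), an apparent improvement. Among the two patients who received both infusions, the counts are 0/2 and 0/2, so nothing changed. Split columns therefore need a within-patient display beside them.

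**The case against.** A reader might infer that the primary question cannot be answered from these tables. The documents do not support that. The objective is the safety and tolerability of multiple doses, not a contrast between the first and second infusion. Once-per-patient incidence over the two-dose course, by dose group, is a valid though incomplete summary of it. Protocol 9.2.3 asks for tabulations by system organ class and preferred term, and the SAP supplies them.

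A reader might also infer that recurrence or worsening is lost altogether. It is not:

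- Listings 16.2.7.1 to 16.2.7.3 show every adverse event and infusion reaction by subject and onset date, and Listing 16.2.5.1 shows dosing.
- Protocol 8.7 requires start and stop for each occurrence of an intermittent event, and distinct onset dates when severity changes over days.
- A patient mild at Dose 1 and severe at Dose 2 appears as severe in Table 14.3.1.10, though not attributed to a dose.
- Serious events, dose-limiting toxicities and discontinuations due to adverse events have their own by-subject listings.
- The Safety Review Committee sees second-dose data as the trial proceeds and does not depend on the report tables.

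Nor do the documents make a per-infusion reaction rate necessary for comparing premedication regimens. Patients reacting per dose group is an accepted summary, and SAP 3.2 plans no hypothesis tests. Two infusions in one patient are not independent units. The frequency of missed second doses is unknown, and Protocol 4.5.3 allows replacement of patients who miss a dose.

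All of this stands. What remains is that the listings give study day from the first dose (SAP 3.11), and Dose 2 falls on Day 28 or Day 21 with a window of up to 2 days. Each reader must therefore match onset to dosing dates by hand and choose a denominator, with no prespecified rule for either.

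**Conclusion.** The point holds as a gap in tabulation. The adverse-event and infusion-reaction tables give valid cumulative incidence over both doses, but change on re-exposure is visible only in listings, and no table gives incidence after Dose 2 among patients who received it.

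The size is an ambiguity within cells: 3, 6 or 10 possible Dose 1/Dose 2 patterns behind an entry of 1, 2 or 3 patients. These counts assume that every affected patient received both doses, and the 36% illustration assumes both rates and independence. They show what the tables cannot distinguish; they do not predict what will be seen. With at most 27 planned patients the hand reconstruction is feasible, so this is a cheap improvement worth making and does not undermine the trial's safety conclusions.

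**What to change.** Keep the planned tables. Then:

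1. In Tables 14.3.1.1 and 14.3.1.7 at least, and preferably also 14.3.1.2 and 14.3.1.3, add two columns: onset from infusion 1 to before infusion 2, and onset from infusion 2 onward. The denominator of each is the patients who received that infusion.
2. In Table 14.3.1.7, among patients who received both infusions, also give the number reacting at the first only, the second only and both. This guards against an apparent improvement caused by patients not re-dosed because of Dose 1 toxicity. Reactions per infusion may be added but are not essential.
3. State how partial or missing onset dates are assigned to an infusion. The imputation rule in SAP 4.5.2 refers to the day of treatment without saying which dose, and limits imputed dates to deciding treatment emergence.
4. State that an event ongoing at Dose 2 that then worsens counts in the Dose 2 column. The severity-change records required by Protocol 8.7 make this workable.

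Onset time and date are already collected (Protocol 8.4), so no new data, visits or protocol amendment are needed. The cost is SAP wording and a little extra programming. The downside is small cells that can be read only descriptively.
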